**Evaluation of Wear Experience with Daily Disposable Water Surface Contact
lenses in habitual Comfilcon A contact lens wearers**

NCT 05096156

Evaluation of Wear Experience with Daily Disposable Water Surface Contact lenses in habitual Comfilcon A contact lens wearers

[name], OD MS

The Ohio State University College of Optometry
Innovation in Vision and Eye care Research Group - iVERG

Purpose

The purpose of this study is to explore the wear experience of current Comfilcon A (Biofinity®) contact lens wearers after they have been fit into Verofilcon A (PRECISION1®) Contact Lenses.

Study Overview

This open-label study is of current Biofinity® (Cooper Vision, San Ramon, CA, USA) contact lens wearers who are satisfied with their lenses. Subjects will be refit into PRECISION1® contact lenses and will wear lenses for approximately 2 weeks. Subjects will return for vision and lens fit assessments and will complete surveys about their wear experience.

Background

Soft daily wear contact lenses are used by an estimated 40.9 million adults in the United States.¹ Contact lenses which are worn for daily wear are considered minimal risk by the FDA, and risks to wearers are minimized by proper lens care and hygiene. Daily disposable contact lenses do not require daily cleaning and overnight storage, which improves the required amount of time to care for contact lenses. In addition, daily disposable contact lenses are associated with less lens deposits, which decreases associated comfort issues in lens wearers, including decreasing the risk of triggering Giant papillary conjunctivitis (GPC) and/or ocular allergic responses in patients.² Additionally, daily disposable contact lens wearers are not likely to expose their lenses to water and tend to have better lens hygiene since these lenses do not require daily cleaning. This is reflected in a study which found less superficial punctate staining and symptoms of dryness when comparing daily disposable contact lens wear with planned replacement lenses.³ The subjects in this study are current satisfied wearers of 1 month planned replacement lenses (Biofinity®) and will be fit into PRECISION1 daily disposable contact lenses, which are less likely to be associated with the already minimal risks of daily contact lens wear.

Key Endpoints:

- Subjective assessment of P1 with CLDEQ-8

- Visual Analog Scale survey of lens wear symptoms (comfort, dryness, vision)

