- Assessment via questionnaire about quality of life, preference, and lens modality experience

Study Time Points:

Visit 1 will be conducted to consent the subject and determine eligibility. Consenting will be conducted via phone call and REDCap and will occur before the subject arrives on site if possible. The participant will verify their current prescription with Biofinity lenses and answer questions about ocular health to further determine eligibility. Participants will also verify that they are happy with their current lenses. Upon reporting to the in-person portion of the visit, visual acuity and an evaluation of the subject's ocular health will occur. Biofinity® lenses will be evaluated and optimized before dispensing a new pair of lenses for approximately 1 week of wear.

Visit 2: Biofinity® contact lens follow up and Precision 1 fitting visit. Patients will verify that they are still satisfied with their current Biofinity® contact lenses in order to proceed and vision, lens fit and ocular health will be assessed. Subjects will then be fit with PRECISION1® Contact Lenses and will complete assessments of initial satisfaction, initial comfort, and initial vision using REDCap. Lenses will be dispensed and a contact lens follow-up visit will be scheduled.

Visit 3: The contact lens follow up visit will occur approximately 2 weeks (± 3 days) following the PRECISION1 lens fitting. Subjects will have visual acuity, an assessment of ocular health, and lens fit completed. Subjects will then complete surveys about their lens wear experience.

Surveys will be completed using REDCap and include:

- CLDEQ-8
- VAS survey of comfort/dryness/vision on a 0 to-100 scale:
 - Overall Quality of vision
 - End of Day Quality of vision
 - Overall comfort
 - End of Day comfort
 - Overall dryness
 - End of Day dryness
- Quality of life/preference, lens modality experience
- Convenience of daily disposable, preference for daily disposable, ease of use
- Satisfaction with P1

Recruitment

Potential subjects may see posters placed on bulletin boards at The Ohio State University or local eye care offices, emails to students, faculty and staff at OSU, online or paper ads, or signs on the OSU buses. A

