search of the electronic medical records of The Ohio State College of Optometry may be done to identify possible subjects who then may be contacted by email or phone with information about the study. Word of mouth referrals by study team members to OSU employees and friends may occur. Emails to alumni of the OSU College of Optometry may be sent for local doctors to notify eligible potential subjects about the study.

Inclusion criteria:

- Subjects must be current Biofinity® spherical lens wearers.
- Subjects must have 20/25 or better distance visual acuity with current lenses.
- Good general health (defined by medication use that has not changed within the last month and the absence of medical conditions or treatments that are deemed confounding to the data as determined by the PI)
- Ability to give informed consent
- Willing to spend time for the study. Subjects will be required to attend three study visits and wear contact lenses on days between study visits.
- Either gender
- Any racial or ethnic origin
- 18 to 40 years of age.

Exclusion criteria:

- No current ocular inflammation or infection as assessed by the study investigator
- Pregnant or lactating females

Consent and Confidentiality

A team member trained in the consent process will provide the consent document for the potential subject to read and will review the procedures with reference to the consent form. The individual will be given provided time to read the consent form and offered the opportunity to ask questions. Participants will be explicitly told that they may stop participation at any time. All subjects will have the capacity to give informed consent. If there is any doubt as to the subject's ability to consent to the study, the subject will be excluded from the study. If the subject agrees to take part in the screening or measurement, he or she will sign and date the most recent IRB-stamped consent as will the team member. The subject will be provided with a copy of the consent form.

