The investigator team is trained in privacy issues and will be reminded of the importance of patient privacy prior to study initiation. Potential study participants will contact us after seeing advertisements, emails or hearing about the study by word of mouth, giving them the choice of whether or not they wish to participate in a study for people with dry eyes. Privacy is protected by limiting information related to study recruitment only, and no other personal or medical information that should be private to the patients. The PHI needed is only for the purposes of this study. It is highly unlikely, indeed extremely remote that the dry eye symptoms or signs are related to private or personal information that should or would be preferred to be kept confidential to the patients. Risk factors for dry eye rarely relate to matters

or conditions that would be personal to the patient such as personal relationships, behaviors or diseases that one prefers to keep private and confidential.

Statistical Analysis and Power Calculation

This small sample size of 30 was chosen for convenience, as this study is not intending to prove superiority, but to study the acceptability of the study lens in previous successful Biofinity® wearers.

Data Management and Security

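### Does an acceptability study of 30 wearers need a designated acceptability endpoint and a written rule for counting subjects who leave before Visit 3?

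*Combined protocol and SAP*

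**What the plan says.** The statistics section is a single sentence. It begins "This small sample size of 30 was chosen for convenience" and gives the reason that "this study is not intending to prove superiority, but to study the acceptability of the study lens". Acceptability is mentioned nowhere else; the Purpose section speaks of exploring wear experience.

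The Key Endpoints are "Subjective assessment of P1 with CLDEQ-8", visual analogue scale (VAS) ratings of comfort, dryness and vision, and a questionnaire on quality of life, preference and lens modality. Under Study Time Points, subjects at Visit 2 "will complete assessments of initial satisfaction, initial comfort, and initial vision using REDCap". Visit 3 falls "approximately 2 weeks (± 3 days) following the PRECISION1 lens fitting", and its survey list includes the Key Endpoint instruments, "Convenience of daily disposable, preference for daily disposable, ease of use" and, as a separate bullet, "Satisfaction with P1".

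Three provisions bear on who has Visit 3 answers:

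- Consent and Confidentiality says participants are told that "they may stop participation at any time".
- Subject Dismissal makes dismissal mandatory for visits missed outside the required time frame. For subjects who cannot give analyzable data, one sentence makes it discretionary and a later one mandatory.
- Data Management and Security says that when a subject is disenrolled, the questionnaires and data forms go into the data binder.

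The section headed Protocol Violations, Discontinuation has no text on discontinuation.

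**The concern.** The one sentence that states an analytic target uses a word that no endpoint carries. CLDEQ-8, the VAS items, preference and satisfaction (initial or at Visit 3) could each be put forward as acceptability once the answers are known. A good rating for daily disposables as a modality could also be presented as acceptance of this particular lens.

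Subjects can also drop out of view. Someone who withdraws, or is dismissed for a late Visit 3, has initial ratings from Visit 2 and no CLDEQ-8, VAS or preference survey on the study lens. If dislike of the lens is a reason for leaving, a completers-only figure flatters it; if departures are for unrelated reasons, the figure could err either way. Without a rule on how these subjects are counted, a reader could not tell how many fitted wearers the result leaves out. The two wordings of the dismissal rule add doubt about who is removed.

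**Working it through.** **What can be reproduced.** The sample size of 30 has no formula behind it and is declared to be a convenience choice, so there is nothing to recompute. The Visit 3 window is 14 − 3 = day 11 to 14 + 3 = day 17. Reading the undefined required time frame in Subject Dismissal as this window is an inference, though a reasonable one: it is the only numeric window in the protocol.

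**Who actually lacks a Visit 3 survey.** No dismissal rule covers a subject who simply stops wearing the lens. Such a subject can attend Visit 3 in window and complete every survey, and that is where a lens-related dislike would be recorded. Only leaving the study or missing the window loses the survey. Problems with analyzable data concern use of equipment and, by the protocol's own account, usually show at screening, before the study lens is dispensed. The survey endpoints do not depend on that equipment.

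**Size, for a proportion.** The documents give no loss rate and no satisfaction rate, so both are assumed. Take 30 dispensed, *m* without Visit 3 answers, and *s* satisfied among 30 − *m* completers. The completers' figure is *s*/(30 − *m*). The bounds over all dispensed run from *s*/30 (every missing subject dissatisfied) to (*s* + *m*)/30 (every missing subject satisfied), a width of *m*/30, or 3.3 points per missing subject. Intervals are exact (Clopper-Pearson) 95%.

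| *m* | *s*/(30 − *m*) | Completers | Exact 95% CI | Half-width | Bounds over 30 |
|---|---|---|---|---|---|
| 1 | 22/29 | 76% | 56 to 90% | 17 points | 73 to 77% |
| 3 | 20/27 | 74% | 54 to 89% | 18 points | 67 to 77% |
| 6 | 18/24 | 75% | 53 to 90% | 18 points | 60 to 80% |

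The largest gap between the completers' figure and a bound is 75 − 60 = 15 points, with 6 lost. That is inside the sampling half-width of about 18 points. With *m* = 0 the gap is zero.

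**Size, for a VAS mean (0 to 100).** Assume missing subjects differ from completers by 20 points and the SD is 20. The all-dispensed mean moves by (*m*/30) × 20:

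- 3 missing: 3/30 × 20 = 2.0 points.
- 6 missing: 6/30 × 20 = 4.0 points.

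The 95% half-width for a mean is *t*/√*n* in SD units: 0.373, 0.396 and 0.422 at *n* = 30, 27 and 24. Multiplied by 20, these give 7.5, 7.9 and 8.4 points. The shifts are about a quarter (2.0/7.9) and a half (4.0/8.4) of the sampling error.

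**The undesignated endpoint.** There is no hypothesis test, threshold or decision that turns on which measure is called acceptability. Satisfaction with the lens and the daily-disposable items are already separate bullets in the Visit 3 list, so reporting the list as written keeps lens and modality apart.

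**The case for a change.** The strongest case for a change is that sampling error is displayed by a confidence interval, while selective loss is not and does not shrink with more subjects. In a study of acceptability, leaving may itself be evidence about the lens. The counting rule can also matter more than in the table above. If 24 subjects accept the lens and every lost subject is among the others, then 3 losses give 24/27 = 88.9% for completers against 24/30 = 80.0% over all dispensed. Six losses give 24/24 = 100% (exact 95% CI 85.8 to 100%) against 80.0%, which lies outside the completers' interval. The remedy would cost only a few sentences and one table.

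Part of this stands. Selective loss is a different kind of error from sampling error, and a report that gave only completers' percentages with no account of the rest would be poor. But the six-loss case needs a fifth of the subjects to leave a wear period of about two weeks and every one of them to have disliked the lens. Nothing in the documents suggests either, and staff are to make reasonable efforts to fit visits to subjects' schedules. Even then, the harm is done only if the report omits the number fitted. The plan does not direct that omission: dismissal from the study is not deletion from the data, and the forms are retained. The freedom to pick a favourable measure is likewise limited, because the Key Endpoints are named in advance and can all be reported.

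**Conclusion.** No change to the plan is needed. The protocol does leave acceptability untied to any one measure and does not say how non-completers are counted, but these are details that the analyst of a 30-subject, single-arm, descriptive study fills in sensibly: report every listed endpoint, and state how many were fitted, how many completed, and why the others did not. No figure in the plan is wrong, and no stated rule is shown to give a wrong result. Under the assumed losses of 1 to 6 subjects with about three-quarters of completers satisfied, the possible shift in a proportion is at most 15 points, within a sampling half-width of about 18. For a VAS mean it is 2.0 to 4.0 points against about 8. The conclusion assumes that losses are not both heavy and wholly lens-related, and that the report gives the number dispensed.

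The discretionary and mandatory sentences in Subject Dismissal do contradict each other and should be reconciled if the text is revised for another reason. They concern problems usually seen before the study lens is dispensed, and no survey result turns on them. The missing discontinuation text under its heading is a drafting omission of the same order.

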the equipment, to name just two causes issues. These issues are usually revealed at the screening assessment visit. Subjects who cannot provide analyzable data will be dismissed for the study. Subjects who do not keep scheduled visits within the required time frame will be dismissed from the study. Study team members will make reasonable efforts to accommodate subjects' schedules.

Protocol Violations, Discontinuation

In the event that a member of the study team or a representative of sponsor becomes aware of a major protocol violation, the IRB shall be notified within 10 working days.

Timeline

IRB submission and approval → Recruitment and Data collection → Data processing and analysis → Final report
6-8 weeks Months 3-4 Month 5 Month 6

References

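### Late attenders are dismissed and early stoppers have no planned exit survey, so the acceptability summary may rest on on-time completers only and read too favourably

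*Combined protocol and SAP*

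**What the plan says.** - **Dismissal.** Subject Dismissal: "Subjects who do not keep scheduled visits within the required time frame will be dismissed from the study". The next sentence promises reasonable efforts to fit visits around subjects' schedules.
- **Visit 3 timing.** Study Time Points places this visit "approximately 2 weeks (± 3 days) following the PRECISION1 lens fitting". It is the only visit with an explicit plus-or-minus window.
- **Surveys.** The Visit 3 paragraph ends: "Subjects will then complete surveys about their lens wear experience". The list that follows, opened by "Surveys will be completed using REDCap and include", covers CLDEQ-8, six VAS items, quality of life, preference and modality items, convenience, and satisfaction with the study lens. These are the key endpoints. No other visit is named for them.
- **Earlier ratings of the study lens.** At the Visit 2 fitting, subjects "will complete assessments of initial satisfaction, initial comfort, and initial vision using REDCap".
- **Stopping.** Consent and Confidentiality: "Participants will be explicitly told that they may stop participation at any time". The protocol describes no exit survey and no record of the reason for stopping.
- **Aim.** Statistical Analysis and Power Calculation gives a convenience sample of 30 and states the purpose as "to study the acceptability of the study lens in previous successful Biofinity® wearers". It names no denominator, analysis set or method for missing data.
- **Data of subjects who leave.** Data Management and Security says how a disenrolled subject's paperwork is filed, not whether the data are analysed.

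**The concern.** Two groups have no planned wear-experience outcome.

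1. **Late responders.** If the required time frame for Visit 3 is the stated window, a subject who could answer on day 18 is dismissed. That reading is an inference, but no other Visit 3 window is given.
2. **Early stoppers.** A subject who gives up the study lens and does not return provides no survey, whether or not the dismissal rule is applied.

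The study asks whether satisfied wearers of one lens find another acceptable, so a subject who abandons the new lens is evidence on that question. If such subjects are more likely to be missing, a summary of those who attend on time overstates acceptability. With a single group, no parallel arm could reveal or offset the loss. A subject who goes back to the habitual lens but attends Visit 3 on time is captured, so the gap concerns leaving the study, not merely leaving the lens.

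**Working it through.** **The plan's own figure.** The sample size of 30 is stated as a convenience choice, with no error rate, power, effect size, standard deviation or dropout behind it. There is nothing to reproduce.

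**Inputs from the protocol.** N = 30; Visit 3 window 14 − 3 = day 11 to 14 + 3 = day 17; VAS items scored 0 to 100.

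**Assumptions.** All 30 are dispensed the study lens (the protocol does not say whether 30 means enrolled, dispensed or completed). The number lost is k = 1, 3 or 6. Some survey item is reduced to favourable or not; the protocol defines no such acceptance measure. Lost subjects would score d = 20 or 30 points worse on a VAS item. None of k, the favourable rates or d comes from the documents.

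**Step 1, bounds on a proportion.** Let x of n = 30 − k completers be favourable, with p = x/n. Over all 30 the true figure lies between x/30 (no lost subject favourable) and (x + k)/30 (all favourable). The width is k/30 whatever the value of p: 1/30 = 3.3 points, 3/30 = 10.0 and 6/30 = 20.0.

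**Step 2, where the completer figure sits.** It is too high by at most p·k/30 and too low by at most (1 − p)·k/30. Intervals are exact (Clopper-Pearson).

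| k | Completers favourable (95% CI) | Range over all 30 | Too high by at most | Too low by at most |
|---|---|---|---|---|
| 1 | 26/29 = 89.7% (72.6 to 97.8) | 86.7% to 90.0% | 3.0 points | 0.3 |
| 3 | 24/27 = 88.9% (70.8 to 97.6) | 80.0% to 90.0% | 8.9 | 1.1 |
| 3 | 20/27 = 74.1% (53.7 to 88.9) | 66.7% to 76.7% | 7.4 | 2.6 |
| 3 | 14/27 = 51.9% (31.9 to 71.3) | 46.7% to 56.7% | 5.2 | 4.8 |
| 6 | 21/24 = 87.5% (67.6 to 97.3) | 70.0% to 90.0% | 17.5 | 2.5 |

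The lopsidedness in the rows near 90% comes from the assumed rate. It is not evidence about this trial.

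**Step 3, a VAS mean.** If the k lost subjects would have averaged d points worse than completers, the completer mean is k·d/30 too favourable: 1 × 20/30 = 0.7 points; 3 × 20/30 = 2.0; 6 × 30/30 = 6.0.

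**Step 4, loss unrelated to the lens.** The expected bias is zero. For k = 3 the standard error grows by √(30/27) = 1.054, that is 5.4%.

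**The case against.** - **The window is inferred, and lateness need not mean dissatisfaction.** Visit timing is described as approximate, staff will accommodate schedules, and no mechanism links attending on day 18 to disliking the lens. This stands in part: for late responders the cost may be precision only. But the rule as written is mandatory and discards answers that subjects are willing to give.
- **The dismissal section may not have been written for this study.** It mentions moving freely to use equipment and is inconsistent on whether subjects with unanalysable data may or will be dismissed. The text still governs, and the early-stopper gap does not depend on it.
- **The early-stopper group is narrow.** Wear lasts about two weeks, subjects agree to three visits, and Visit 2 ratings and adverse event reports exist. This stands as a limit on size. However, the Visit 2 ratings precede the wear period, and adverse event reports do not record preference, convenience or ordinary dissatisfaction.
- **This argues from silence.** Consent documents and data forms are not in the text reviewed and could hold a withdrawal item. It is fair to say only that the protocol describes none.
- **No summary of completers is actually specified, and the magnitudes are all assumed.** Both are true. In each row of the table the lower bound also lies inside the completer interval. But that interval describes sampling error and does not correct selective loss, and a descriptive study still needs a stated denominator.

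None of these supplies a reading under which late responders' or early stoppers' wear experience is collected.

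**Conclusion.** The concern holds and should be fixed. Followed as written, the plan collects no post-wear survey from subjects who stop early and do not return or, on the natural reading of the window, from those who attend late. The bias is conditional: too favourable if loss is related to dissatisfaction, absent in expectation otherwise. Its size cannot be determined from the documents. Under the assumed losses, each lost subject widens the possible range of a proportion by 3.3 points. The largest overstatement in the cases shown is 3.0 points with one lost and 17.5 points with six lost. For a VAS mean the cases shown run from 0.7 to 6.0 points. Confidence is moderate, because the amount of loss and its link to dissatisfaction are both unknown.

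**What to change.** 1. Do not end survey collection for visit timing alone. Keep late Visit 3 surveys, flag them, and repeat the summary without them. This concerns survey data only; clinical follow-up and continued participation remain for the study team to decide.
2. At early exit, offer the existing REDCap survey remotely, with one added item on the reason for stopping. Remote contact is already in use: "Consenting will be conducted via phone call and REDCap". Subjects who decline are reported as unknown.
3. Take all subjects dispensed the study lens at Visit 2 as the denominator and report four counts: completed, stopped for lens-related reasons, stopped for other reasons, and unknown.
4. Show exit surveys separately from two-week surveys, or give the summary with and without them. For any proportion reported from a preference or satisfaction item, add bounds with non-responders counted each way.

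The cost is protocol wording, IRB approval of the revision, one REDCap item and one small table, with no extra subjects or on-site visits. Survey timing will vary somewhat more, some exit surveys will be declined, and the reported result may be slightly less favourable. Reasons for stopping may not be recoverable afterwards, so the change needs to be in place before subjects leave.
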